8.1.2 Disease Parameters

Measurable disease. Measurable lesions are defined as those that can be accurately measured in at least one dimension (longest diameter to be recorded) as ≥ 20 mm by chest x-ray or ≥ 10 mm with CT scan, MRI, or calipers by clinical exam. All tumor measurements must be recorded in millimeters (or decimal fractions of centimeters).

Note: Tumor lesions that are situated in a previously irradiated area might or might not be considered measurable. If the investigator thinks it appropriate to include them, the conditions under which such lesions should be considered must be defined in the protocol.

Malignant lymph nodes. To be considered pathologically enlarged and measurable, a lymph node must be ≥ 15 mm in short axis when assessed by CT scan (CT scan slice thickness recommended to be no greater than 5 mm). At baseline and in follow-up, only the short axis will be measured and followed.

Non-measurable disease. All other lesions (or sites of disease), including small lesions (longest diameter < 10 mm or pathological lymph nodes with ≥ 10 to < 15 mm short axis), are considered non-measurable disease. Bone lesions, leptomeningeal disease, ascites, pleural/pericardial effusions, lymphangitis cutis/pulmonitis, inflammatory breast disease, abdominal masses (not followed by CT or MRI), and cystic lesions are all considered non-measurable.

Note: Cystic lesions that meet the criteria for radiographically defined simple cysts should not be considered as malignant lesions (neither measurable nor non-measurable) since they are, by definition, simple cysts.

'Cystic lesions' thought to represent cystic metastases can be considered as measurable lesions, if they meet the definition of measurability described above. However, if non-cystic lesions are present in the same participant, these are preferred for selection as target lesions.

Target lesions. All measurable lesions up to a maximum of 2 lesions per organ and 5 lesions in total, representative of all involved organs, should be identified as **target lesions** and recorded and measured at baseline. Target lesions should be selected on the basis of their size (lesions with the longest diameter), be representative of all involved organs, but in addition should be those that lend themselves to reproducible repeated measurements. It may be the case that, on occasion, the largest lesion does not lend itself to reproducible measurement in which circumstance the next largest lesion which can be measured reproducibly should be selected. A sum of the diameters (longest for non-nodal lesions, short axis for nodal lesions) for all target lesions will be calculated and reported as the baseline sum diameters. If lymph nodes are to be included in the sum, then only the short axis is added into the sum. The baseline sum diameters will be used as reference to further characterize any objective tumor regression in the measurable dimension of the disease.

Non-target lesions. All other lesions (or sites of disease) including any measurable lesions over above the 5 target lesions should be identified as **non-target lesions** and should also be recorded at baseline. Measurements of these lesions are not required, but the presence, absence, or in rare cases unequivocal progression of each should be noted throughout follow up

8.1.3 Methods for Evaluation of Disease

All measurements should be taken and recorded in metric notation using a ruler, calipers, or a digital measurement tool. All baseline evaluations should be performed as closely as possible to the beginning of treatment and never more than 4 weeks before the beginning of the treatment.

The same method of assessment and the same technique should be used to characterize each identified and reported lesion at baseline and during follow-up. Imaging-based evaluation is preferred to evaluation by clinical examination unless the lesion(s) being followed cannot be imaged but are assessable by clinical exam.

Clinical lesions. Clinical lesions will only be considered measurable when they are superficial (e.g., skin nodules and palpable lymph nodes) and ≥ 10 mm in diameter as assessed using calipers (e.g., skin nodules). In the case of skin lesions, documentation by color photography, including a ruler to estimate the size of the lesion, is recommended.

Chest x-ray. Lesions on chest x-ray are acceptable as measurable lesions when they are clearly defined and surrounded by aerated lung; however, CT is preferable.

Conventional CT and MRI. This guideline has defined measurability of lesions on CT scan based on the assumption that CT thickness is 5mm or less. If CT scans have slice thickness greater than 5 mm, the minimum size of a measurable lesion should be twice the slice thickness. MRI is also acceptable in certain situations (e.g. for body scans).

Use of MRI remains a complex issue. MRI has excellent contrast, spatial, and temporal resolution; however, there are many image acquisition variables involved in MRI, which greatly impact image quality, lesion conspicuity, and measurement. Furthermore, the availability of MRI is variable globally. As with CT, if an MRI is performed, the technical specifications of the scanning sequences used should be optimized for the evaluation of the type and site of disease. Furthermore, as with CT, the modality used at follow-up should be the same as was used at baseline and the lesions should be measured/assessed on the same pulse sequence. It is beyond the scope of the RECIST guidelines to prescribe specific MRI pulse sequence parameters for all scanners, body parts, and diseases. Ideally, the same type of scanner should be used and the image acquisition protocol

should be followed as closely as possible to prior scans. Body scans should be performed with breath-hold scanning techniques, if possible.

FDG-PET. While FDG-PET response assessments need additional study, it is sometimes reasonable to incorporate the use of FDG-PET scanning to complement CT scanning in assessment of progression (particularly possible 'new' disease). New lesions on the basis of FDG-PET imaging can be identified according to the following algorithm:

(a) Negative FDG-PET at baseline, with a positive FDG-PET at follow-up is a sign of PD based on a new lesion.

(b) No FDG-PET at baseline and a positive FDG-PET at follow-up: If the FDG-PET at follow-up corresponds to a new site of disease confirmed by CT, this is PD. If the positive FDG-PET at follow-up is not confirmed as a new site of disease on CT, additional follow-up CT scans are needed to determine if there is truly progression occurring at that site (if so, the date of PD will be the date of the initial abnormal FDG-PET scan). If the positive FDG-PET at follow-up corresponds to a pre-existing site of disease on CT that is not progressing on the basis of the anatomic images, this is not PD.

(c) FDG-PET may be used to upgrade a response to a CR in a manner similar to a biopsy in cases where a residual radiographic abnormality is thought to represent fibrosis or scarring. The use of FDG-PET in this circumstance should be prospectively described in the protocol and supported by disease-specific medical literature for the indication. However, it must be acknowledged that both approaches may lead to false positive CR due to limitations of FDG-PET and biopsy resolution/sensitivity.

Note: A 'positive' FDG-PET scan lesion means one which is FDG avid with an uptake greater than twice that of the surrounding tissue on the attenuation corrected image.

PET-CT. At present, the low dose or attenuation correction CT portion of a combined PET-CT is not always of optimal diagnostic CT quality for use with RECIST measurements. However, if the site can document that the CT performed as part of a PET-CT is of identical diagnostic quality to a diagnostic CT (with IV and oral contrast), then the CT portion of the PET-CT can be used for RECIST measurements and can be used interchangeably with conventional CT in accurately measuring cancer lesions over time. Note, however, that the PET portion of the CT introduces additional data which may bias an investigator if it is not routinely or serially performed.

MIBG (meta-iodobenzylguanidine). The following is recommended, to assure high quality images are obtained.

Patient preparation: Iodides, usually SSKI (saturated solution of potassium iodide), are administered to reduce thyroidal accumulation of free radioiodine, preferably beginning the day prior to injection and continuing for 3 additional days (4 days total). For infants and children, one drop t.i.d. is sufficient, for adolescents 2 drops t.i.d., and for adults 3 drops t.i.d. Participants and/or parents are asked about exposure to potential interfering agents. If none is noted, an indwelling intravenous line is established. The dose of MIBG is administered by slow intravenous injection over 90 seconds.

Images from the head to the distal lower extremities should be obtained.

I-123MIBG scintigraphy is performed to obtain both planar and tomographic images.

Planar: Anterior and posterior views from the top of the head to the proximal lower extremities are obtained for 10 minutes at 24 hours and occasionally at 48 hours following injection of 10 mCi/1.7 square meters of body surface area (~150 µCi/kg, maximum 10 mCi). Anterior views of the distal lower extremities are adequate. A large field of view dual head gamma camera with low energy collimators is preferred.

SPECT: Most participants receiving I-123 MIBG also undergo SPECT at 24 hours, using a single or multi-headed camera with a low energy collimator. The camera is rotated through 360 degrees, 120 projections at 25 seconds per stop. Data are reconstructed using filtered back projections with a Butterworth filter and a cut off frequency of 0.2-0.5. SPECT/CT may be performed at institutions with this capacity.

Ultrasound. Ultrasound is not useful in assessment of lesion size and should not be used as a method of measurement. Ultrasound examinations cannot be reproduced in their entirety for independent review at a later date and, because they are operator dependent, it cannot be guaranteed that the same technique and measurements will be taken from one assessment to the next. If new lesions are identified by ultrasound in the course of the study, confirmation by CT or MRI is advised. If there is concern about radiation exposure from CT, MRI may be used instead of CT in selected instances.

Endoscopy, Laparoscopy. The utilization of these techniques for objective tumor evaluation is not advised. However, such techniques may be useful to confirm complete pathological response when biopsies are obtained or to determine relapse in trials where recurrence following complete response (CR) or surgical resection is an endpoint.

Tumor markers. Tumor markers alone cannot be used to assess response. If markers are initially above the upper normal limit, they must normalize for a participant to be considered in complete clinical response. Specific guidelines for both CA-125 response (in recurrent ovarian cancer) and PSA response (in recurrent prostate cancer) have been published [*JNCI* 96:487-488, 2004; *J Clin Oncol* 17, 3461-3467, 1999; *J Clin Oncol* 26:1148-1159, 2008]. In addition, the Gynecologic Cancer Intergroup has developed CA-125 progression criteria which are to be integrated with objective tumor assessment for use in first-line trials in ovarian cancer [*JNCI* 92:1534-1535, 2000].

Cytology, Histology. These techniques can be used to differentiate between partial responses (PR) and complete responses (CR) in rare cases (e.g., residual lesions in tumor types, such as germ cell tumors, where known residual benign tumors can remain).

The cytological confirmation of the neoplastic origin of any effusion that appears or worsens during treatment when the measurable tumor has met criteria for response or stable disease is mandatory to differentiate between response or stable disease (an effusion may be a side effect of the treatment) and progressive disease.

8.1.4 Response Criteria

8.1.4.1 Evaluation of Target Lesions

Complete Response (CR): Disappearance of all target lesions. Any pathological lymph nodes (whether target or non-target) must have reduction in short axis to <10 mm.

Partial Response (PR): At least a 30% decrease in the sum of the diameters of target lesions, taking as reference the baseline sum diameters.

Progressive Disease (PD): At least a 20% increase in the sum of the diameters of target lesions, taking as reference the smallest sum on study (this includes the baseline sum if that is

the smallest on study). In addition to the relative increase of 20%, the sum must also demonstrate an absolute increase of at least 5 mm. (Note: the appearance of one or more new lesions is also considered progressions).

Stable Disease (SD): Neither sufficient shrinkage to qualify for PR nor sufficient increase to qualify for PD, taking as reference the smallest sum diameters while on study.

8.1.4.2 Evaluation of Non-Target Lesions

Complete Response (CR): Disappearance of all non-target lesions and normalization of tumor marker level. All lymph nodes must be non-pathological in size (<10 mm short axis).

Note: If tumor markers are initially above the upper normal limit, they must normalize for a patient to be considered in complete clinical response.

Non-CR/Non-PD: Persistence of one or more non-target lesion(s) and/or maintenance of tumor marker level above the normal limits.

Progressive Disease (PD): Appearance of one or more new lesions and/or *unequivocal progression* of existing non-target lesions. *Unequivocal progression* should not normally trump target lesion status. It must be representative of overall disease status change, not a single lesion increase.

Although a clear progression of “non-target” lesions only is exceptional, the opinion of the treating physician should prevail in such circumstances, and the progression status should be confirmed at a later time by the review panel (or Principal Investigator).

8.1.4.3 Evaluation of New Lesions

The finding of a new lesion should be unequivocal (i.e. not due to difference in scanning technique, imaging modality, or findings thought to represent something other than tumor (for example, some ‘new’ bone lesions may be simply healing or flare of pre-existing lesions). However, a lesion identified on a follow-up scan in an anatomical location that was not scanned at baseline is considered new and will indicate PD. If a new lesion is equivocal (because of small size etc.), follow-up evaluation will clarify if it truly represents new disease and if PD is confirmed, progression should be declared using the date of the initial scan on which the lesion was discovered.

8.1.4.4 Evaluations of Best Overall Response

The best overall response is the best response recorded from the start of the treatment until disease progression/recurrence (taking as reference for progressive disease the smallest measurements recorded since the treatment started). The patient's best response assignment will depend on the achievement of both measurement and confirmation criteria.

For Participants with Measurable Disease (i.e., Target Disease)

Target Lesions	Non-Target Lesions	New Lesions	Overall Response	Best Overall Response when Confirmation is Required*
CR	CR	No	CR	≥4 wks Confirmation**
CR	Non-CR/Non-PD	No	PR	≥4 wks Confirmation**
CR	Not evaluated	No	PR	

PR	Non-CR/Non-PD/not evaluated	No	PR	
SD	Non-CR/Non-PD/not evaluated	No	SD	Documented at least once ≥ 4 wks from baseline**
PD	Any	Yes or No	PD	no prior SD, PR or CR
Any	PD***	Yes or No	PD	
Any	Any	Yes	PD	

* See RECIST 1.1 manuscript for further details on what is evidence of a new lesion.
 
** Only for non-randomized trials with response as primary endpoint.
 
*** In exceptional circumstances, unequivocal progression in non-target lesions may be accepted as disease progression.
 
Note: Participants with a global deterioration of health status requiring discontinuation of treatment without objective evidence of disease progression at that time should be reported as “symptomatic deterioration.” Every effort should be made to document the objective progression even after discontinuation of treatment.
				

For Participants with Non-Measurable Disease (i.e., Non-Target Disease)

Non-Target Lesions	New Lesions	Overall Response
CR	No	CR
Non-CR/non-PD	No	Non-CR/non-PD*
Not all evaluated	No	not evaluated
Unequivocal PD	Yes or No	PD
Any	Yes	PD

* 'Non-CR/non-PD' is preferred over 'stable disease' for non-target disease since SD is increasingly used as an endpoint for assessment of efficacy in some trials so to assign this category when no lesions can be measured is not advised
		

8.1.5 Duration of Response

Duration of overall response: The duration of overall response is measured from the time measurement criteria are met for CR or PR (whichever is first recorded) until the first date that recurrent or progressive disease is objectively documented (taking as reference for progressive disease the smallest measurements recorded since the treatment started, or death due to any cause. Participants without events reported are censored at the last disease evaluation).

Duration of overall complete response: The duration of overall CR is measured from the time measurement criteria are first met for CR until the first date that progressive disease is objectively documented, or death due to any cause. Participants without events reported are censored at the last disease evaluation.

Duration of stable disease: Stable disease is measured from the start of the treatment until the criteria for progression are met, taking as reference the smallest measurements recorded since the treatment started, including the baseline measurements.

8.1.6 Survival outcomes

Overall Survival: Overall Survival (OS) is defined as the time from randomization (or registration) to death due to any cause, or censored at date last known alive.

Progression-Free Survival: Progression-Free Survival (PFS) is defined as the time from randomization (or registration) to the earlier of progression or death due to any cause. Participants alive without disease progression are censored at date of last disease evaluation.

Time to Progression: Time to Progression (TTP) is defined as the time from randomization (or registration) to progression, or censored at date of last disease evaluation for those without progression reported.

8.2 Other Response Parameters

In addition to RECIST 1.1, irRECIST (a modification of irRC to use RECIST 1.1 criteria (Nishino et al.) will be independently assessed as a measure of response and outcome measurement.

8.2.1 Disease Parameters

Disease assessments (assessments of target, non-target, and non-measurable lesions) and methodology of assessment follows RECIST 1.1 and is as detailed in section 8.1.2 and 8.1.3.

8.2.2 Response Criteria

The major differences in response criteria are as outlined here but please refer to Nishino et al, 2013 for further details:

New Measurable lesions

In order to be selected as new measurable lesions (≤ 2 lesions per organ, ≤ 5 lesions total, per timepoint), new lesions must meet criteria as defined for baseline target lesion selection and meet the same minimum size requirements of 10 mm in long diameter and minimum 15 mm in short axis for new measurable lymph nodes. New measurable lesions shall be prioritized according to size, and the largest lesions shall be selected as new measured lesions.

Measurement of total tumor burden

The longest diameters of non-nodal target and new non-nodal measurable lesions, and short axes of nodal target and new nodal measurable lesions will be recorded. Together they determine the Total Measured Tumor Burden (TMTB) at follow-up.

Non-target lesions

The RECIST 1.1 definitions for the assessment of non-target lesions apply. The response of non-target lesions primarily contributes to the overall response assessments of irCR and irNon-CR/Non-PD (irNN). Non-target lesions do not affect irPR and irSD assessments. Only a massive and unequivocal worsening of non-target lesions alone, even without progress in the TMTB is indicative of irPD.

Measurement of response

irCR: complete disappearance of all measurable and non-measurable lesions. Lymph nodes must decrease to < 10 mm in short axis. Confirmation of response is not mandatory. irPR: decrease of $\geq 30\%$ in TMTB relative to baseline

non-target lesions are irNN, and no unequivocal progression of new non-measurable lesions.

irSD: failure to meet criteria for irCR or irPR in the absence of irPD.

irNN: no target disease was identified at baseline and at follow-up the patient fails to meet criteria for irCR or irPD.

irPD: minimum 20% increase and minimum 5 mm absolute increase in TMTB compared to nadir, or irPD for non-target or new non-measurable lesions. Confirmation of progression is recommended minimum 4 weeks after the first irPD assessment.

irNE: used in exceptional cases where insufficient data exists.

irND: in adjuvant setting when no disease is detected (not applicable here).

For further details, see Nishino et. Al. 2013.

9 Statistical Plan

SCLC provides an opportune setting to evaluate the potential importance of variability in PD-L1 expression and its influence on optimizing timing of checkpoint inhibition. All extensive-stage SCLC patients are treated with chemotherapy and recent data suggests added benefit to consolidation thoracic radiation¹⁰.

The proposed study seeks to evaluate pembrolizumab therapy initiated at different times during the course of SCLC treatment: a) up front, in conjunction with initiation of chemotherapy, b) starting after one cycle of chemotherapy, c) starting after completion of 1st line chemotherapy, d) starting after completion of consolidation thoracic radiation therapy and/or PCI. Treatment with pembrolizumab will be preceded by biopsy for evaluation of PD-L1 expression with correlative evaluation of changes in PD-L1 expression (relative to diagnostic biopsy) and changes in other tissue- and blood-based biomarkers and immune markers. The study is based on the following hypotheses:

- 1) PD-L1 expression is dynamic and can increase with exposure to chemotherapy and/or radiation
- 2) PD-L1 expression influences efficacy of pembrolizumab=
- 3) Pembrolizumab can improve outcomes in SCLC

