3.3 Secondary Study Endpoints

- To evaluate progression-free survival with the addition of pembrolizumab to standard therapy
 - endpoint: to evaluate median progression-free survival in overall population with stratification by cohort as compared to historical control of 5.4 months³¹
- To evaluate overall survival with the addition of pembrolizumab to standard therapy
 - Endpoint: to evaluate median overall survival in overall population with stratification by cohort as compared to historical control of 9.5 months.³¹
- To evaluate response rates by RECIST 1.1 and irRC (as adapted to RECIST 1.1³²) with the addition of pembrolizumab to standard therapy (for cohort A only)
 - Endpoint: response rate at 6 and 12 weeks after initiation of pembrolizumab therapy as measured by RECIST 1.1 and irRC (as adapted to RECIST 1.1³²)

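### In section 8.2.2 the irPR line conflicts with the general rule on non-target lesions and with the irNN definition, so the same scan can be scored irPR or irSD

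*Combined protocol and SAP*

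**What the plan says.** Section 8.2.2 sets out irRECIST as a modification of RECIST 1.1. Four of its statements bear on irPR.

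- **irPR line.** A decrease of at least 30% "in TMTB relative to baseline", followed after a line break by "non-target lesions are irNN, and no unequivocal progression of new non-measurable lesions".
- **General rule on non-target lesions.** "Non-target lesions do not affect irPR and irSD assessments". Only massive, unequivocal worsening of non-target disease counts against the participant, and it does so as irPD.
- **irNN definition.** "irNN: no target disease was identified at baseline and at follow-up the patient fails to meet criteria for irCR or irPD".
- **irSD definition.** "irSD: failure to meet criteria for irCR or irPR in the absence of irPD".

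irCR requires every measurable and non-measurable lesion to have gone. Non-target lesions are assessed with the RECIST 1.1 categories (CR, Non-CR/Non-PD, PD).

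The RECIST 1.1 table in section 8.1.4.4 gives one permitted non-target status for the target PR and target SD rows: "Non-CR/Non-PD/not evaluated".

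The endpoint served is in section 3.3: "response rate at 6 and 12 weeks after initiation of pembrolizumab therapy as measured by RECIST 1.1 and irRC" as adapted to RECIST 1.1. Section 3.3 restricts it to cohort A.

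**The concern.** A partial response should not become harder to reach because the non-target disease did better. Read with irSD as the remainder, the irPR line does this. It admits persisting non-target disease and leaves out non-target disease that has cleared. The general rule, a few lines earlier in the same section, gives the opposite answer.

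Two assessors who each follow a sentence of section 8.2.2 could therefore classify the same scan differently. At stake is the irRECIST response rate at 6 and 12 weeks in cohort A. The situation is plausible. Section 8.1.2 caps target lesions at two per organ and five in total, so any further lesions in extensive-stage disease are non-target, and section 6.7.1.1 describes robust response to chemotherapy, which cohort A receives. Section 9.1 also compares baseline PD-L1 with response, but does not say whether response there means RECIST 1.1 or irRECIST.

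**Working it through.** The plan states no response rate, power or threshold for this endpoint, so there is no figure to reproduce. The check applies the written rules to defined records.

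**Inputs.** The irCR, irPR, irSD and irNN rules and the general non-target rule are from section 8.2.2. The cohort size of 15 is from section 4.4. The 12 participants per group assumed to yield results are from section 9.1.

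**Readings.** No irPD is assumed throughout, and irNN is taken as the lesion-level status Non-CR/Non-PD.

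- A: irPR needs non-target status irNN, literally.
- A2: as A, but the condition counts as met when there are no non-target lesions.
- B: the general rule governs, and non-target status does not affect irPR.

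| TMTB change | Non-target lesions | A | A2 | B |
|---|---|---|---|---|
| -100% | all gone, or none at baseline | irCR | irCR | irCR |
| -100% | persisting | irPR | irPR | irPR |
| -50% or -30% | persisting | irPR | irPR | irPR |
| -50% or -30% | all gone | **irSD** | **irSD** | **irPR** |
| -50% or -30% | none at baseline | irSD | irPR | irPR |
| -20% | any of these | irSD | irSD | irSD |

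The fourth row is the clear conflict: both versions of the irPR line give irSD and the general rule gives irPR. The third row has the same TMTB change with a worse non-target result, yet is irPR on every reading. The fifth row depends on whether the condition is taken as met when there is nothing to assess.

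**The irNN definition.** It requires that there was no target disease at baseline. Such a participant has no baseline target burden from which to fall by 30%. The term as defined therefore cannot serve as a condition inside the irPR line.

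**Effect on the rate.** Moving k participants between irSD and irPR changes the response rate by 100 × k/n points.

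| k | n = 15 | n = 12 |
|---|---|---|
| 1 | 100 × 1/15 = 6.7 | 100 × 1/12 = 8.3 |
| 2 | 100 × 2/15 = 13.3 | 100 × 2/12 = 16.7 |
| 3 | 100 × 3/15 = 20.0 | 100 × 3/12 = 25.0 |

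The documents do not give k. The range 1 to 3 is an assumption.

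**The RECIST 1.1 table.** Target PR or target SD combined with non-target CR, or with no non-target lesions at baseline, matches no row without new lesions. The table assigns no overall response there.

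**The case against.** The strongest reply is that the plan contains the correct rule. An assessor who follows the general sentence scores every affected participant irPR, and nothing is understated. This stands to the extent that misscoring is possible, not certain. It does not remove the contradiction, because nothing in the section says which sentence takes precedence.

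It can also be said that the section is an outline that refers to a cited publication for details, and that a connecting word may have been lost at the line break before the non-target condition. The referral is for further detail and does not say that the publication overrides the written rule. A lost connective would not reconcile the condition with the irNN definition.

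The small reach of the problem is a fair point. It touches one secondary endpoint in one cohort, irRECIST is assessed in addition to RECIST 1.1, and the recorded lesion measurements would allow categories to be derived again.

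A reader might infer four stronger things, which the documents do not support.

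- *That nobody with target disease could ever be irPR.* This applies the participant-level definition of irNN inside the irPR line. The section also uses irNN as shorthand for a non-target status: "The response of non-target lesions primarily contributes to the overall response assessments of irCR and irNon-CR/Non-PD (irNN). An assessor would most naturally read it that way.
- *That participants with no non-target lesions at baseline are plainly misscored.* The condition can be read as met when there are no such lesions, so this case is ambiguous.
- *That a large bias can be calculated from an assumed response rate and an assumed share of responders without remaining non-target disease.* Neither input is in the documents, and such a share would include complete responders, who are irCR on every reading.
- *That the wording creates a false gap between RECIST 1.1 and irRECIST rates.* The RECIST 1.1 table is silent on the same combinations. It leaves them unassigned and does not put them in a wrong category, so no direction of difference follows.

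**Conclusion.** The irPR rule in section 8.2.2 is wrong as written: it contradicts the section's general rule on non-target lesions and uses irNN in a sense that the section's own definition excludes. The clear consequence is limited to participants whose TMTB falls by at least 30% with measurable disease remaining and whose non-target lesions have all disappeared. They can be scored irSD under one sentence and irPR under another.

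Each such participant changes the irRECIST response rate in cohort A by 6.7 points (n = 15) or 8.3 points (n = 12). If 1 to 3 participants were affected, which is an assumption, the change would be 6.7 to 20.0 points or 8.3 to 25.0 points. The effect arises only if assessors follow the irPR line over the general sentence. The primary PD-L1 endpoint is not touched. A correction is worth making because the contradiction is explicit and costs nothing to remove.

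**What to change.** In section 8.2.2, reword the definition along these lines: *irPR: TMTB at least 30% below baseline, irCR not met, and no irPD arising from non-target or new non-measurable lesions.* This agrees with the general rule and also settles the case with no non-target lesions at baseline. Keep irNN as a participant-level category for those without target disease, and do not use it as a condition for irPR.

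For consistency, extend the non-target entry in the target PR and target SD rows of the section 8.1.4.4 table to include CR and none at baseline.

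The cost is one definition and two table rows. No further data, scans or participants are needed. The wording should be settled before responses are scored; any already scored can be derived again from the recorded measurements.
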